## 7.3.8 Safety endpoints

AEs will be encoded using the MedDRA thesaurus in the most recent version available at the beginning of the study. This version will be used throughout the entire study. Updates of the MedDRA thesaurus will not be applied afterwards.

All AEs will be listed by subject, user or other persons, date and time since last treatment. Incidence of AEs will be summarized by preferred term (PT) and system organ class (SOC), and also by intensity, duration causal relationship to the device or procedure, and seriousness.

The frequency and occurrence rate, maximum intensity, overall duration, and seriousness of injection site reactions within four weeks (28 days) after baseline treatment, after repeat-treatment injection, respectively, and 6 weeks in case of touch-up treatment, will be summarized by device.

The number and percentage of subjects, user or other persons with at least one device deficiency will be summarized. Details concerning device deficiencies will be listed by treatment group and subject.

Urine pregnancy tests will be listed only.

The data will be presented for the SAF using frequency tables.

#### 7.3.9 Multicentre trial

This study will take place in approximately 16 investigation sites. Inclusion of subjects is planned to be as equally distributed as possible between the sites (see section 6.3.1 for details).

Possible country (or geographical cluster) and study site effects will not be included in the primary analysis, but will be evaluated on an exploratory level by tabulation of the primary and key secondary endpoints by country (or geographical cluster) and study site, respectively.

Any pooling of study sites with few subjects as well as pooling of countries in geographical clusters will be agreed and specified in the SAP before database lock.

#### 7.3.10 Analysis of subgroups

The primary analysis will be based on the total trial population. Besides the total study population, the following subgroups will be analyzed by descriptive statistical methods for the primary and the main secondary effectiveness endpoints:

- Injection equipment: Needle versus cannula
- Gender: Female versus male
- Fitzpatrick skin type
- Race and ethnicity
- Age groups

In order to gather information on potential heterogeneity of treatment effects between the different subgroups, an exploratory analysis will be performed using logistic regression models with subgroup as covariate and a treatment by subgroup interaction. 95% confidence intervals will be calculated for the treatment difference in each subgroup and presented in a forest plot.

In addition, incidence of AEs will be summarized by preferred term (PT) and system organ class (SOC) within all of the above-mentioned subgroups. Frequency and occurrence rate of injection site reactions will be summarized within all of the above-mentioned subgroups.

The detailed statistical analysis of subgroups will be described in the statistical analysis plan (SAP).

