# 6.1.2 Randomization

The randomization will be performed at the Baseline visit (Visit 2), after final confirmation of subject's eligibility. Treatment assignment will be pre-planned according to a computer-generated randomization schedule in a 2:1 ratio (test device : comparator device). The schedule will contain the following treatment assignments, which will be randomly allocated to sequential randomization scheme:

- Test device: saypha® VOLUME Lidocaine
- Comparator device:

The randomization information will assign the subject to one of the treatment groups. In addition, a minimum of 100 subjects randomized to the test device will be treated with either needle or cannula.

Only unblinded site staff performs the randomization via a randomization function of the eCRF.

Neither the blinded evaluator at the site nor the central independent photographic reviewer will have access to the randomization system (see section 6.1.3 for details). The randomization number will be documented in the eCRF.

The exact procedure for obtaining a randomization number/treatment assignment for a subject will be provided to each investigational site before the study is initiated by training and will be described in a separate manual or other appropriate document.

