The rater blinding regarding treatment group in initial treatment will remain in effect until study data base lock. The blinded evaluator at the site will be trained on the MVDSS and NLF-SRS prior to start of the investigation during the investigator meeting, a live WebEx with a sponsor medical consultant, or through review of a recording of the WebEx. Open questions by on-site located raters will be answered during the pre-study visits; further training on the scale will be also performed during site pre-study visits, if needed. The independent blinded photographic reviewers will be trained on the MVDSS prior to their assessments of the photographs.

In addition, the improvement of midface volume deficit will also be evaluated centrally by using computerized volume change measurement based on the 3D photographic images. The quantified data of the volume change measurement provide additional evidence confirming the effectiveness of the test device for the indication to be treated (see section 6.4.12).

The time point for definition of the primary endpoint (Week 24 after last injection of the initial treatment phase) was selected based on clinical experience with other HA fillers and will be corroborated by earlier and later observations (see Table 1 and Table 3 for details). Difference of one grade on this scale is considered to be clinically meaningful since it can be visually recognized by various observers as demonstrated during validation of the scale.

The clinical relevance of the investigation will be also supported by several (other) secondary effectiveness endpoints (see section 5.3), related to global aesthetic improvement (by using the modified GAIS) [35] and subject's satisfaction with outcome (overall and the cheeks by using FACE-QTM scales).[36, 37]

Information on occurrence of pain will be primarily obtained by collection of AEs, with additional insight into pain intensity being obtained directly after the injection using a semi-quantitative 11-point Numeric Pain Rating Scale (NRPS).[38].

Touch-up treatments are allowed in the investigation, and the treating investigator will determine the appropriate injection volume and injection technique and equipment (i.e., needle/cannula) based on his/her clinical experience (see sections 6.2). A minimum of 100 subjects randomized to the test device will be treated with either needle or cannula. Use of either needle or cannula is based on the treating investigator's medical decision.

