## Precautions

- is packaged for single-patient use. Do not resterilize. Do not use if package is open or damaged. In such case follow instructions given in section 14.9.
- injectable gel is a clear, colorless gel without particulates. In the event that the content of a syringe shows signs of separation and/or appears cloudy, do not use the syringe. In such case follow instructions given in section 14.9.
- Directions for Use may adversely impact the sterility, homogeneity, and performance of the product. In such case follow instructions given in section 14.9.
- As with all transcutaneous procedures, dermal filler implantation carries a risk of infection. Standard precautions associated with injectable materials should be followed.
- The safety has been established for use in patients between 35 and 65 years of age for cheek augmentation. However, the filler is indicated for cheek augmentation to correct age related volume deficit in the midface in adults over the age of 21 (see InC#1 in section 6.3.3.1).
- Subjects may experience late onset nodules with use of dermal fillers, including (see section 14 for documentation and reporting obligations for AEs).
- Subjects who experience skin injury near the site of the section of the section of the section may be at a higher risk for adverse events (see section 14 for documentation and reporting obligations for AEs).
- The safety of **sector** with cannula for cheek augmentation has not been established in subjects with Fitzpatrick Skin Types V and VI. However, for this study, inclusion of subjects with Fitzpatrick Skin Types IV to VI is encouraged (see section 6.6).

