## 7.1 Sample size and hypothesis

The primary outcome measures for effectiveness will be evaluated by means of a one-sided two-group Farrington-Manning test for the difference between proportions with the following hypotheses:

- H0:  $pA pB \le -10\%$
- H1: pA pB > 10%

At this, pA is the percent response rate for saypha® VOLUME Lidocaine based on the blinded evaluator's live assessment at Week 24 after last injection of initial treatment phase, while pB is the corresponding response rate for the saypha . Thus, a negative value for this difference means that the response rate of saypha® VOLUME Lidocaine is lower than the response rate for

The non-inferiority margin is -10%.

Further assumptions for sample size calculation:

- Response rate at Week 24 for saypha® VOLUME Lidocaine is 85.6%
- Response rate at Week 24 for the second se
- Randomization ratio 2:1

Based on these assumptions, 437 subjects (saypha® VOLUME Lidocaine: n=291,

 $\alpha$  of 2.5%. Assuming 10% exclusion from PPS results in 486 subjects to be randomized. Adding 6% screen failures yields approximately 516 subjects to be enrolled.

Concerning FAS, it is expected that only very few subjects will be regarded as non-responder due to missing data for the primary effectiveness endpoint. Response rates at Week 24 after last injection of the initial treatment phase may be slightly smaller than assumed above. Due to the increased sample size in the FAS (more than 10% compared to the PPS) it is expected that the power will be adhered as specified above.

Sample size calculation was done using SAS® version 9.4.

Approximately 300 subjects are estimated to qualify for repeat treatment.

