## 7.3.7 Effectiveness endpoints

#### Primary effectiveness endpoint

The PPS and the FAS will be both considered equally important for the primary analysis. The analysis of the primary endpoint will be performed on the PPS (primarily) and FAS. Confirmatory testing will be performed in a hierarchical ordering. Non-inferiority is demonstrated only if the results are consistent for both analysis populations.

Subjects with missing baseline MVDS score and / or missing MVDS score at Week 24 after last injection of the initial treatment phase will be considered as non-responders for the primary analysis on the FAS.

To calculate the primary outcome measure, the improvement over Baseline in the MVDS score assessed live by the blinded evaluator at the site at Week 24 after last injection of the initial treatment phase by subtracting the Midface Scale grade obtained at Baseline. The proportion of subjects with MVDS score improvement of  $\geq 1$  point will be then calculated for each treatment group.

The primary outcome measure for effectiveness will be evaluated by means of a one-sided two-group Farrington-Manning test of proportions with the following hypotheses:

- H0:  $pA pB \le d0$
- $\circ \qquad H1: pA pB > d0.$

At this, pA is the response rate for saypha® VOLUME Lidocaine and pB is the response rate for , and d0 equals to -0.1. Thus, a negative value for this difference means that the response rate of saypha® VOLUME Lidocaine is lower than the response rate for In addition to this, the response rates for both treatment groups along with their Clopper-

Pearson exact 95% CIs will be tabulated.

The study decision will be based on a Farrington-Manning-statistics with a one-sided type I error rate level of 0.025.

In addition, **sensitivity analyses** of the primary effectiveness endpoint will be performed on the FAS addressing the different reasons for non-adherence and covering the following aspects (among others) to underline the robustness of the results:

- Complete case analysis: In this analysis only those subjects will be included for whom the primary endpoint could be calculated;
- Subjects with non-allowed concomitant medication / treatments before Week 24 after last injection of the initial treatment phase may be regarded as non-responder.
- Multiple imputation under MNAR assumption for imputing missing MVDS scores at Week 24 assessed live by the blinded evaluator.

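### Section 7.3.10 analyses needle versus cannula as a baseline subgroup, but an unblinded injector chooses the equipment, so its device comparison is not randomised and may reflect selection

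*Protocol*

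**What the plan says.** Protocol section 7.3.10 names five subgroup factors, the first being "Injection equipment: Needle versus cannula". To look for differing treatment effects, "an exploratory analysis will be performed using logistic regression models with subgroup as covariate and a treatment by subgroup interaction". A 95% confidence interval for the treatment difference in each subgroup goes into a forest plot. No factor is treated differently from the others, and further detail is deferred to the SAP.

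Other sections describe how equipment is assigned:

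- Section 6.1.2: "Only unblinded site staff performs the randomization via a randomization function of the eCRF". It names no equipment stratum, and neither does section 7.9.
- Section 6.5.2 lists randomisation before device administration at Visit 2.
- Section 6.1.4: "Use of either needle or cannula is based on the treating investigator's medical decision". Section 6.1.3 says that the treating investigator is aware of the allocation.
- Section 6.4.10 has the equipment used documented with the injection details. No section asks for intended equipment before randomisation.
- Section 6.2.2 requires the same device at touch-up but not the same equipment. The Amendment 1 log (19.1) confirms that the equipment requirement was withdrawn.

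**The concern.** Gender, age, race/ethnicity and skin type are fixed before allocation, so within each level randomisation still makes the two device groups comparable. Equipment is selected by someone who knows the device, and it can change at touch-up after the early result has been seen. Suppose the injector steers harder faces towards one type of equipment with one device but not with the other. The cannula row then compares different kinds of subject between arms, and so does the needle row, with the bias in the opposite direction.

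The hypothesis of interest is that the device effect is the same with needle and cannula. The hypothesis actually tested is that the odds ratios are equal between groups formed after allocation. The second can be false when the first is true, and real heterogeneity can be masked in the same way. A reader of the forest plot has no sign that these two rows differ in kind from the rest.

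**Working it through.** **Control on the primary test.** The plan gives no operating figure for the subgroup interaction, so the only figure to reproduce is the primary power. Inputs: "The non-inferiority margin is -10" percentage points; "The study decision will be based on a Farrington-Manning-statistics with a one-sided type I error rate level of 0.025"; 291 test subjects out of 437 evaluable, hence 146 comparator; test response 85.6% (section 7.1). The comparator rate is blacked out and is assumed to be 85.6%. Farrington-Manning power with the restricted null variance is then 83.6% (86.8% at a comparator rate of 85.0%, 77.7% at 86.5%), in line with the power above 83% in the Amendment 5 log. 437/0.9 = 485.6, that is 486 randomised. The primary analysis is not in question.

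**Set-up for the interaction.** 324 test and 162 comparator subjects (section 6.3.1). No device effect and no equipment effect. Response depends only on whether a face is easy or hard, and averages 85.6%. The test is a two-sided 5% Wald test of the treatment-by-equipment log odds ratio, which is the interaction in the saturated logistic model. The prognostic rates and selection rules are assumptions; the protocol gives none.

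With hard share *h*, response *pE* (easy) and *pH* (hard), and cannula probability *sE* and *sH*, response in an arm's cannula group is

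[(1−h)·sE·pE + h·sH·pH] / [(1−h)·sE + h·sH]

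The needle group uses 1−sE and 1−sH instead.

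**One case by hand (strong selection, test arm only).** h = 0.3, pE = 0.93, pH = 0.6833 (0.7×0.93 + 0.3×0.6833 = 0.856). Test arm sE = 0.35, sH = 0.85; comparator 0.5 and 0.5.

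- Test cannula share: 0.7×0.35 + 0.3×0.85 = 0.50, so 162 subjects on each equipment.
- Test cannula response: (0.2279 + 0.1743)/0.50 = 80.4%. Test needle: (0.4232 + 0.0308)/0.50 = 90.8%. Comparator: 85.6% in both groups.
- False device differences: −5.2 points (cannula), +5.2 points (needle).
- Log odds ratio interaction: ln(0.8042/0.1958) − ln(0.9078/0.0922) − 0 = −0.874.
- Variance: 1/25.51 + 1/13.56 + 2/9.98 = 0.313, so SE = 0.560 and z = −1.56.
- Approximate rejection: Φ(−1.96 + 1.56) = 35%. Simulation with 10,000 trials gives 33.8%.

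**Simulated rejection, h = 0.3 (10,000 trials each).** The two columns are response 93%/68% and 90%/75% for easy/hard faces.

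| Rule for choosing cannula | 93/68 | 90/75 |
|---|---|---|
| Random, 50% in both arms | 4.8% | 4.5% |
| Prognosis-driven, same rule in both arms | 4.1% | 4.5% |
| Share differs (50% v 20%), unrelated to prognosis | 3.9% | 3.7% |
| Mild, test arm only (45% easy, 62% hard) | 7.1% | 5.6% |
| Strong, test arm only (35% easy, 85% hard) | 33.8% | 14.5% |
| Opposite rules in the two arms | 86.1% | 42.9% |

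**Second parameterisation** (half the subjects with good prognosis; response 93%/78.2% or 96%/75.2%; 6,000 runs). Same selection in both arms: 4.6-5.0%. Test-arm cannula use of 60% in good- and 40% in poor-prognosis subjects, against 50% of each in the comparator arm: 7.0-8.8%. With 70% and 30% against 50% of each: 14.1-23.6%, with false differences of 3 to 4 points.

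**Does the minimum of 100 protect?** Section 6.1.2 says "a minimum of 100 subjects randomized to the test device will be treated with either needle or cannula". In the case worked by hand the test arm has 162 subjects on each equipment, so the minimum is met and the bias remains.

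**If intent were fixed before allocation**, the choice could follow prognosis but not device. That is the second row of the table: 4.1-4.5%, with zero bias in the subgroup differences.

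**The case against.** The strongest reply is that nothing in the protocol shows differential selection by prognosis, and without it there is no bias. This largely stands. Three features might be read as proof that it occurs:

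- The minimum of 100 is stated for the test arm only. That affects how many subjects receive each equipment, not which ones. Simulated shares of 50% v 20% and 33% v 60% gave 3.5-4.5% rejection and no bias.
- For the comparator, the precautions in section 6.2.4.2 say that safety "with cannula for cheek augmentation has not been established in subjects with Fitzpatrick Skin Types V and VI". Types V and VI are about 10% of planned enrolment (section 6.3.2), and nothing says that skin type predicts response. If the comparator arm never used cannula in these types and the test arm used it in half, rejection is 4.3% with no prognostic effect and 6.9% with an assumed 20-point response gap.
- Table 15 ties serial puncture to the needle for the comparator and leaves technique open for the test device. It does not direct particular faces to particular equipment. The comparator is also approved for midface cannula injection (section 2.2).

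A reader might also infer that the 14-34% rejection rates are expected, that the false differences should be set against the 10-point margin, or that this subgroup is meant to support a claim for both types of equipment. The documents support none of these. The selection strengths are assumed, no margin or decision rule applies within subgroups, and the Amendment 1 rationale for the minimum is safety data in a real-life setting.

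The appeal to the SAP does not stand. Section 7.3.10 already fixes the factor, the interaction and the intervals, and no later rule based only on equipment used can restore comparability. The exploratory label limits the strength of the claim but does not remove selection. It is fair to add that needle-versus-cannula results within an arm are also confounded, hence the label proposed below.

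**Conclusion.** The point holds as a flaw in a stated exploratory analysis. Equipment is not a baseline factor, and the device contrast within needle or within cannula is not randomised. That the choice follows allocation is inferred from the visit order and the absence of any earlier record; the protocol does not say when the investigator decides.

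The size of any bias cannot be determined from the protocol. The device-specific features it does contain give about 4-7% rejection, within the nominal-to-mild range. Larger figures need strong selection on prognosis that differs by device, for which there is no evidence. Knowledge of the device alone is not enough. The primary analysis uses the whole population and is untouched. This is a cheap improvement, not a threat to the trial's conclusion.

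**What to change.** In section 7.3.10, remove injection equipment from the factors given a treatment-by-subgroup interaction and an unadjusted between-device confidence interval. Report needle and cannula results descriptively within each device arm, classified by the equipment used at the first injection (which avoids reclassification at touch-up), and label them non-randomised. If a between-device contrast by equipment is kept, adjust it for baseline MVDSS grade, Fitzpatrick type, age and site, all already collected, and state that it remains open to selection. Leave the interaction analysis as it is for gender, age, race/ethnicity and skin type.

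Recording intended equipment in the eCRF before randomisation would be the cleaner design, but it is probably too late: the Amendment 5 log describes recruitment of all subjects in the past tense.

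Cost: a wording change, with one exploratory interaction test and two forest-plot rows dropped or downgraded. The safety summaries by equipment are kept.

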## 7.4 Subject data listings

All recorded data will be presented in subject data listings.

## 7.5 Missing data

Adverse events with unknown onset times will be counted as post device administration AEs. AEs with missing relationship to device will be counted as related AEs (ADEs).

Concerning statistical evaluation of the primary effectiveness endpoint (primary analysis, sensitivity analyses) missing data may be regarded as non-response.

In addition, there will be no imputation of missing values. All data will be analyzed as they appear in the data base.

## 7.6 Software used for statistical analysis

The SAS software version 9.4 or higher will be used for the statistical analysis and for the reporting of this study.

## 7.7 Deviations from the planned statistical analysis

Any deviations from the planned statistical analysis have to be discussed in the final study report and should be defined in the SAP. If the deviation has any impact on the effectiveness analysis, the deviation has to be specified in an amendment to the CIP.

## 7.8 Amendments

If an amendment impacts the integrity of the clinical investigation, the data collected before and after the amendment must be analyzed statistically to assess the effect of the amendment on effectiveness or safety analysis. This analysis must be included in the clinical investigation report.

#### 7.9 Randomization

The randomization list will be prepared by a biostatistician using SAS, Procedure PLAN. The randomization list is a document that consists of randomization numbers, which uniquely assign each subject to one of the two devices at a 2:1 ratio (test device: comparator device). Randomization will be performed using randomly permuted blocks.

